7.1.2 Dosing and Administration

The research team will first measure each participant's head using the 10-20 system to determine the electrode locations. Participants will then be fitted with the 3 electrodes for stimulation: two 5x5cm electrodes placed over F3 (left frontal cortex, standard 10-20 EEG coordinated) and F4 (right frontal cortex), and one 5x7cm electrode placed over C2 (midline, central). Electrodes will be carbon rubber, with Ten20 conductive paste applied. During stimulation, the participant will be in a relaxed and experimentally controlled state by watching a nature movie (such as Reefscapes). One session of stimulation will be performed per day, for up to 40-minutes. Before each stimulation session, a single-channel eyes open and eyes closed resting state EEG will be performed to individualize the treatment frequency.

The stimulation waveforms used in this study are tACS at the individual peak alpha frequency at 1 mA zero-to-peak amplitude both at F3 and F4, achieved via a splitter cable to distribute 2 mA between the two sites. Stimulation includes a ramp-in and ramp-out of 20 seconds, with a maximum of 40-minutes of stimulation at an amplitude of 1 mA per electrode, for a total of 2440 seconds of stimulation.

Research personnel will be thoroughly trained and have training documented on the transcranial stimulation device and will be present during all stimulation sessions. To monitor side effects of stimulation a stimulation effects questionnaire will be administered after each stimulation session. At D5, a systematic interview for side-effect is administered.

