8. STUDY INTERVENTION DISCONTINUATION AND PARTICIPANT DISCONTINUATION/WITHDRAWAL

8.1 DISCONTINUATION OF STUDY INTERVENTION

Discontinuation from the week of stimulation does not mean discontinuation from the study, and remaining study procedures should be completed as indicated by the study protocol. If a clinically

significant finding is identified (including, but not limited to changes from baseline) after enrollment, the investigator or qualified designee will determine if any change in participant management is needed.

The study intervention (i.e., the 5 consecutive days of stimulation) will be discontinued for the following reasons:

- A participant develops significantly increased suicidal risk, as determined by an acute assessment by [name] or [name].
- A participant has an ASRM score greater than or equal to 6.
- The participant misses a single day of stimulation and is unable to make it up at the end of the stimulation week.
- Any clinical adverse event (AE), laboratory abnormality, intercurrent illness or other medical condition, or situation occurs such that continued participation in the study would not be in the best interest of the participant.
- The participant meets any exclusion criteria (either newly developed or not previously recognized).

If the participant withdraws from the intervention, the participant will be contacted and invited for the FU1 survey questionnaires and for the FU2 follow-up assessment including all respective questionnaires. These assessments are not intended as a clinical follow-up with the participants but serve research purposes only.

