9.1.2 Self-Report Assessments

- 1. The Quick Inventory of Depressive Symptomatology (QIDS) is a 16-item, self-report rating inventory that measures characteristic attitudes and symptoms of depression and will be used to monitor the severity of the patient's depression throughout the study.
- 2. The Quality of Life Enjoyment and Satisfaction Questionnaire, short form (Q-LES-Q-SF)[17] is a self-report questionnaire that assesses quality of life.
- 3. Stimulation side-effect questionnaires are administered after every stimulation session. Systematic query of side effects across all major organ systems is administered at D5.

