9.2.3 Adverse Event Assessment

A self-report form of sensory experiences associated with stimulation and side-effects will be administered at D1-D5. In addition, a structured interview probing for the experience of adverse events will be administered at D5. [name] or [name] will use the completed interview to assess the severity of the adverse event and its potential relationship to the study intervention.

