9.3.4 TIME PERIOD AND FREQUENCY FOR EVENT ASSESSMENT AND FOLLOW-UP

The occurrence of an adverse event (AE) or serious adverse event (SAE) may come to the attention of study personnel during study visits, or the study participant may report AE or SAEs outside of a scheduled study visit. All AEs including local and systemic reactions not meeting the criteria for SAEs will be captured on the appropriate case report form (CRF). Information to be collected includes event description, time of onset, clinician's assessment of severity, relationship to study product (assessed only by those with the training and authority to make a diagnosis), and time of resolution/stabilization of the event. All AEs occurring while on study must be documented appropriately regardless of relationship. All AEs will be followed to adequate resolution. Any medical condition that is present at the time that the participant is screened will be considered as baseline and not reported as an AE. However, if the study participant's condition deteriorates at any time during the study, it will be recorded as an AE. Changes in the severity of an AE will be documented to allow an assessment of the duration of the event at each level of severity to be performed. AEs characterized as intermittent require documentation of onset and duration of each episode.

Research personnel will record all reportable events with start dates occurring any time after informed consent is obtained until 7 (for non-serious AEs) or 30 days (for SAEs) after the last day of study participation. Events will be followed for outcome information until resolution or stabilization. All AEs including local and systemic reactions not meeting the criteria for SAEs will be captured on the appropriate case report form (CRF). Information to be collected includes event description, time of onset, clinician's assessment of severity, relationship to study product (assessed only by those with the training and authority to make a diagnosis), and time of resolution/stabilization of the event. All AEs occurring while on study must be documented appropriately regardless of relationship. All AEs will be followed to adequate resolution.

Of note, common experiences associated with the application of low-amplitude electric current to the scalp such as phosphenes and tingling sensation are captured with a daily questionnaire. These events are only considered AEs if they are reported as bothersome or untoward by the participant.

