10.4.4 SAFETY ANALYSES

As discussed in *Section 8.2, Safety and Other Assessments* safety will be assessed with the C-SSRS, an adverse effects questionnaire, and the Altman Self-Rating Mania Scale (ASRM).

The C-SSRS will be used to assess suicide risk. If a participant's responses have an elevated risk, the participant will be contacted, and an acute assessment will be completed if deemed necessary by Dr.

[name] or [name] (as described above). Any verified increases in suicidal ideation will be described in counts/percentages. The C-SSRS is administered at the screening visit and at the 14-day follow up.

The stimulation questionnaire will be administered at D1-D5 after stimulation. This questionnaire solicits ratings of 11 possible sensory experiences ("flickering light") and adverse effects ("scalp pain") associated with electrical stimulation, on a scale of 0 (absent), 1 (low), 2(medium), and 3 (high). Intensity of sensory experiences and adverse effects will be described with mean and standard deviation.

The Altman Self-Rating Mania Scale (ASRM) will be used to assess any development of mania over the course of treatment. A ASRM score of greater than 6 indicates the possible development of a manic episode. Any participant who scores greater than 6 on the ASRM will be assessed by [name] or [name]. Any verified manic episode will be described in counts/percentages.

The Adverse Events Structured Interview will be administered by research personnel at D5 and whenever a participant spontaneously reports a potential AE during trial participation. This interview solicits open-ended descriptions of 13 possible adverse effects a participant may experience in any clinical trial as well as one question of 'any other experiences'. Responses will be reviewed by the clinician and rated as described in **Section 8.3.** Severity per adverse effect will be described with mean and standard deviation.

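### The structured adverse-event interview is scheduled only at D5, so it has no pre-stimulation baseline, does not prompt for general AEs in follow-up, and may miss some early stoppers

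*Combined protocol and SAP*

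**What the plan says.** Four places in the text give the timing of the interview, and all say D5:

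- Section 7.1.2: "At D5, a systematic interview for side-effect is administered".
- Section 9.1.2: "Systematic query of side effects across all major organ systems is administered at D5".
- Section 9.2.3: "a structured interview probing for the experience of adverse events will be administered at D5".
- Section 10.4.4: "The Adverse Events Structured Interview will be administered by research personnel at D5 and whenever a participant spontaneously reports a potential AE". It adds that the interview covers 13 prompted effects and one open question, and that severity per effect will be summarised by mean and standard deviation.

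The Schedule of Activities shows one mark for the interview, under D5.

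Section 9.3.4 sets the rules for what counts. On baseline: "Any medical condition that is present at the time that the participant is screened will be considered as baseline and not reported as an AE". Deterioration during the study is an AE. Events are recorded from consent "until 7 (for non-serious AEs) or 30 days (for SAEs) after the last day of study participation".

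For people who stop stimulation, Section 8.1 first says in general terms that the rest of the protocol's procedures should still be done. It then gives a specific instruction: "the participant will be contacted and invited for the FU1 survey questionnaires and for the FU2 follow-up assessment". D5 is not named, and neither FU1 nor FU2 carries the interview in the schedule.

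**The concern.** The trial has one arm and no blinding, so a participant's own state before stimulation is the only internal comparator for a symptom found at D5. Pre-existing complaints are foreseeable. Section 3.1 lists sleep disturbance and cognitive impairment among the features of MDD and mentions side effects of drug treatment, and Section 7.4 allows concomitant antidepressants and other medication. An interview that ranges across organ systems can be expected to pick some of these up, although the 13 items are not listed. Without a reading of the same items before stimulation, the baseline and deterioration rules in Section 9.3.4 cannot be applied to them in a structured way.

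After D5 the way general AEs are found changes from prompted to volunteered, yet Section 10.4.4 describes one summary for both. A participant who leaves during the stimulation week may contribute nothing to the interview data. The safety results could therefore carry errors in opposite directions, too high from old complaints and too low from unprompted follow-up and missing interviews, with no data to separate them.

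**Working it through.** The plan states no figure on this point, so the check is mainly a reading of the schedule, followed by a count of the people affected.

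**1. Coverage of the schedule**

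- Contacts after screening: D1 to D5 (5) and FU1 to FU7 (7), so 12.
- Scheduled interviews: 1 of 12, at D5. Before stimulation: 0. In follow-up: 0 of 7.
- Time from D5 to FU7 (D89): 89 - 5 = 84 days.
- The other stimulation-related instrument, the per-session questionnaire, also ends at D5 (Section 10.4.4).

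**2. What does continue after D5**

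- ASRM at FU1 to FU7 (Schedule of Activities).
- C-SSRS at follow-up; Section 10.4.4 names the 14-day visit.
- Suicide items of the HDRS-17 and QIDS (Section 9.2.1).
- General AEs: Section 9.3.4 relies on events becoming known at visits or being reported, and names no prompted instrument.

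The gap is therefore in prompted elicitation of general AEs, not in all safety assessment.

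**3. What exists at baseline**

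Section 9.1 documents medical history, diagnoses and concomitant therapies at screening. That identifies known conditions. It does not record the presence and severity of the 13 prompted effects, which a new-or-worse comparison needs.

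**4. Who can miss the D5 interview**

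Section 8.1 leaves D5 unclear for people who stop stimulation but stay in the study. Sections 6.5 (two consecutive missed sessions) and 9.2.2 (mania during the stimulation week) end participation altogether, possibly before D5.

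The relevant rate is failure to finish the stimulation week. Section 10.2 reports that 30 of 32 finished it in the earlier trial:

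- Rate: (32 - 30)/32 = 2/32 = 6.25%; Clopper-Pearson 95% CI 0.8% to 20.8%.
- Applied to 35: 35 × 0.0625 = 2.2, about 2 people; range 0.3 to 7.3.
- Chance of at least one: 1 - 0.9375^35 = 0.90.

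Section 10.2's other rate, 80% completing all study sessions, gives 35 × 0.20 = 7. It includes losses in follow-up (26/32 = 81% completed both follow-up sessions), after the D5 interview would have been done, so it is not the right rate here.

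**5. What two missing interviews could do (extreme illustration)**

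Suppose both early stoppers had a given effect, nobody else did, and neither was interviewed. The interview data would show 0/33 (95% upper limit 10.6%) where the true count is 2/35 = 5.7% (95% CI 0.7% to 19.2%).

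**The case against.** The strongest reply is that a prompted interview at the end of a five-day exposure, with further interviews triggered by any report, is defensible for a pilot. Most of the safeguards behind it are real:

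- The interview is also used "whenever a participant spontaneously reports a potential AE during trial participation". Someone who stops because of poor tolerability will usually have said so, and that triggers it.
- Staff attend every session, and an 11-item questionnaire follows each one, so an early stopper still has ratings for the sessions received.
- Section 9.3.4 already has a baseline rule and a deterioration rule and records time of onset. Investigators also grade relatedness (Section 9.3.3.2).

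These points narrow the concern without removing it. The trigger depends on the participant speaking up, the questionnaire covers only sensory and adverse effects of stimulation, and the rules lack a structured baseline for the 13 items.

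A reader might also infer more than the documents support:

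- *That nothing is elicited after D5.* Mania and suicidality are actively assessed in follow-up.
- *That up to 7 of 35 would lack the interview.* That uses the wrong completion rate (step 4).
- *That the people most likely to have had an AE are lost.* The spontaneous-report trigger covers many of them. Those left are people who stop silently or are withdrawn.
- *That a D5 AE rate is biased.* Section 10.4.4 plans a mean and standard deviation of severity for the interview, not a rate.
- *That this is the first study of the device.* Section 7.1.1 describes earlier use of the XCSITE 100 and says the Pro version has identical stimulation hardware. Section 5.2 calls the treatment novel, not the device.

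**Conclusion.** The point holds as a specific, inexpensive improvement to safety measurement. Followed as written, the plan would mix pre-existing complaints into the D5 severity summary, pool prompted with volunteered events, and leave some early stoppers without an interview.

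The certain part is the schedule: one interview in 12 contacts, with none before stimulation and none in the 84 days after D5. The early-stopper part is about 2 of 35 (95% CI about 0.3 to 7.3) at risk of having no interview. This assumes that all 35 consented participants start stimulation and that the earlier trial's non-completion rate carries over. That rate pools its treatment and control frequencies, and Section 10.2 does not say when its two non-completers stopped. The documents do not show how many early stoppers would still attend D5.

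The share of D5 findings that predate stimulation cannot be calculated from the documents, and the direction of the net error is unknown.

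**What to change.** In the Schedule of Activities and Sections 8.1 and 9.2.3, add the existing interview:

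- on D1, after consent and before stimulation;
- at FU2, and at FU4 if wanted, both already in person;
- at the stopping visit, or FU2 at the latest, for anyone who stops stimulation before D5.

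In Section 10.4.4:

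- count an interview item as treatment-emergent only if it is new or worse than at D1;
- alongside the planned severity summary, give counts and percentages among all participants who received any stimulation, the denominator Section 10.4.3 already uses for feasibility;
- report prompted and spontaneous AEs separately.

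The cost is wording changes and a few minutes per visit, with an existing instrument and existing staff. The reported AE count will probably rise, because prompting finds more events. The D1 reading should be in place before enrolment starts, since it cannot be recovered later.

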9.3.3 CLASSIFICATION OF AN ADVERSE EVENT

9.3.3.1 SEVERITY OF EVENT

All adverse events (AEs) will be assessed by the principal investigator and/or co-investigator(s) using the following guidelines:

- **Mild** Events require minimal or no treatment and do not interfere with the participant's daily activities.
- **Moderate** Events result in a low level of inconvenience or concern with the therapeutic measures. Moderate events may cause some interference with functioning.
- Severe Events interrupt a participant's usual daily activity and may require systemic drug therapy or other treatment. Severe events are usually potentially life-threatening or incapacitating. Of note, the term "severe" does not necessarily equate to "serious".

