10.4 STATISTICAL ANALYSES

10.4.1 GENERAL APPROACH

All testing described below assumes a significance threshold of alpha = 0.05. Continuous data will be described using means and standard deviations, while categorical data will be described using counts/percentages.

There will be no pre-specified covariates described in this protocol. Data will be assessed for normality and, if deemed necessary, corrective procedures will be applied (e.g., log normalization).

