10.4.3 ANALYSIS OF THE SECONDARY ENDPOINT (RESPONSE AND REMISSION RATE, FEASIBILITY)

We will compute the response and remission rates for the sample. There is no statistical testing applicable for this outcome since there are no groups to compare.

We will compute the fraction of participants who complete stimulation by dividing the number of people who received 5-days of stimulation by the total number of participants who received any amount of stimulation.

As applicable, 95% confidence intervals will be computed to describe precision of the estimate.

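### Adverse-event severity is graded in words but summarised by mean and SD, and that summary can fail to show a severe event

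*Combined protocol and SAP*

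**What the plan says.** Section 10.4.4 describes the Adverse Events Structured Interview, given at D5 and whenever a participant spontaneously reports a possible event: "This interview solicits open-ended descriptions of 13 possible adverse effects a participant may experience in any clinical trial", plus one catch-all question. The answers are then graded: "Responses will be reviewed by the clinician and rated as described in" Section 8.3. The summary follows: "Severity per adverse effect will be described with mean and standard deviation".

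In the current numbering, 8.3 is Lost to Follow-up. The intended section is 9.3. The same one-number offset occurs where 10.4.4 cites 8.2 for Safety and Other Assessments (now 9.2), where 10.4.5 cites 9.4.1 for the General Approach (now 10.4.1), and where 11.1.7.1 cites 8.3 for AE reporting.

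Section 9.3.3.1 defines mild, moderate and severe in words only, for example "Moderate events may cause some interference with functioning". No numeric codes are attached.

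Section 10.4.1 sets the general rule: "categorical data will be described using counts/percentages". Section 10.4.4 keeps to it for verified increases in suicidal ideation and for mania: "Any verified manic episode will be described in counts/percentages".

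**The concern.** A three-grade verbal rating is categorical, so the plan's rule calls for counts and percentages. AE severity gets a mean and SD instead, and section 10 nowhere explicitly lists a count of participants per adverse effect or per grade.

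The statistic is also undefined. The plan does not say what number each grade receives, whether unaffected participants enter as zero, or which rating counts when a participant is interviewed more than once or an event changes grade.

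In a single-arm pilot of at most 35 people, how many had each adverse effect, and how badly, is a basic safety result. A summary that can look the same with and without a severe event, or that leaves out how many were affected, does not deliver it.

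The stimulation side-effect questionnaire is a separate instrument with stated scores of 0 to 3. Its mean and SD are not at issue.

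**Working it through.** The plan states no figure to reproduce here. The check asks whether the planned summary can separate data with a severe event from data without one.

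**Inputs.** The three grades come from section 9.3.3.1. Sample sizes come from section 10.2: 35 consented (the upper limit on the number treated) and 28 completers (a smaller n for comparison). The codes are assumed, because the plan gives none.

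**Formulas.** Mean = Σx/n. SD = √[(Σx² − (Σx)²/n)/(n − 1)].

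**Reading A (assumed): absent 0, mild 1, moderate 2, severe 3; all treated participants averaged.**

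- Three moderate: Σx = 3×2 = 6; Σx² = 3×4 = 12.
- Three mild and one severe: Σx = 3×1 + 3 = 6; Σx² = 3×1 + 9 = 12.

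Both sums agree, so mean and SD agree exactly and more decimals do not help.

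- n = 35: mean 6/35 = 0.171; SD √[(12 − 36/35)/34] = 0.568.
- n = 28: mean 6/28 = 0.214; SD √[(12 − 36/28)/27] = 0.630.

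A second pair: two mild plus three moderate, and five mild plus one severe, both give Σx = 8 and Σx² = 14. At n = 35 that is mean 0.229, SD 0.598.

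These are not isolated cases. Enumerating all grade distributions, 528 distinct mean/SD pairs at n = 35, and 325 at n = 28, fit data both with and without a severe event.

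**Reading B (assumed): mild 1, moderate 2, severe 3; only affected participants averaged.**

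- The first pair now separates: {2, 2, 2} gives mean 2.0, SD 0; {1, 1, 1, 3} gives mean 1.5, SD 1.0.
- If the number affected is not reported, ties return. One mild plus one moderate gives mean 1.5, SD √0.5 = 0.707. Six mild, three moderate and one severe give mean 15/10 = 1.5, SD √[(27 − 225/10)/9] = 0.707.
- Incidence is not shown: three or ten moderate events both give mean 2.0, SD 0.
- A single event has no SD.

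**Dependence on the codes.** Twenty-four mild, three moderate and one severe give 1.18 (SD 0.48) with codes 1/2/3, and 1.21 (SD 0.63) with codes 1/2/4. The same data give different results under a choice the plan leaves open.

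**Counts instead.** First pair at n = 35, with exact (Clopper–Pearson) 95% intervals:

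| Data | Affected | Severe |
|---|---|---|
| Three moderate | 3/35 = 8.6% (1.8–23.1%) | 0/35 (0–10.0%) |
| Three mild, one severe | 4/35 = 11.4% (3.2–26.7%) | 1/35 = 2.9% (0.1–14.9%) |

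The severe event is visible at once.

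**The case against.** The strongest reply is that section 10.4.1 already covers occurrence. Whether a participant had an adverse effect is categorical, so the general rule would yield a count of those affected without 10.4.4 repeating it. Once that count is known, the exact ties disappear: number affected, Σx and Σx² together fix the three grade counts. This is correct for unrounded values. But it needs the codes to be known, depends on a count that 10.4.4 does not list, and asks the reader to solve for grades that could simply be tabulated. Rounding can also bring ties back: among 28 affected, 27 moderate plus one severe and 27 moderate plus one mild both print as 2.0 (0.2) at one decimal.

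The coding and the all-treated denominator in Reading A are indeed assumptions. They are needed only because the plan supplies neither.

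It is also fair that individual events are not lost. Section 9.3.4 requires that "All AEs occurring while on study must be documented appropriately regardless of relationship", with severity on the case report form. Section 11.1.6 has the principal investigator review all AEs and sends every SAE or unanticipated AE to the IRB and sponsor. Many severe events would be reported that way. However, section 9.3.3.1 itself notes that severe need not mean serious. A severe, non-serious, anticipated event could fall outside those reports and also be invisible in the planned summary.

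Finally, an exact interval for every adverse effect is optional; counts by grade alone cure the defect.

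**Conclusion.** The concern holds. As written, section 10.4.4 applies a mean and SD to an uncoded verbal category, contrary to section 10.4.1, and leaves the codes, the denominator and the handling of repeated ratings undefined.

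The consequence is that the summary can fail to show a severe event, not that it must. Under Reading A the tie is exact (0.171 and 0.568 at n = 35). Under Reading B grades can be recovered if the number affected and unrounded values are given, but the sentence requires neither.

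The defect is confined to the planned safety summary. Data collection, individual event reporting, the primary analysis and the sample size are unaffected. It should be corrected before the analysis. Confidence in the mismatch is high, because it rests on the plan's own text; the numerical illustrations rest on the stated coding assumptions.

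**What to change.** Replace the sentence in section 10.4.4 with wording such as:

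> For each adverse effect, the number and percentage of participants with the event will be reported by worst severity grade, with all participants who received any stimulation as the denominator, and an exact 95% confidence interval for any event.

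Taking the worst grade settles repeated interviews and changes in severity. The denominator is the one section 10.4.3 already uses for feasibility: "the total number of participants who received any amount of stimulation". Because section 9.3.4 records events from consent onwards, and section 8.2 allows for people who consent but are never stimulated, any events in that group should be listed separately. The interval may be dropped if the table becomes unwieldy.

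Correct the reference from Section 8.3 to 9.3 in the same edit. The mean and SD for the 0-to-3 stimulation questionnaire may stay; counts by maximum rating over D1–D5 are an optional addition.

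The cost is one sentence and one table layout. The grades are already collected for each event.
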